| Objectives | 
Study 1:
 
 • To investigate whether the skin autofluorescence (SAF) levels increase over time in prevalent and incident people on peritoneal dialysis (PD) and haemodialysis (HD). • To investigate one-year survival in relation to increased SAF levels. • To determine the most important factors associated with changes in SAF over time. • To investigate the association of increased SAF levels with morbidity, changes in visual function, health-related quality of life and nutritional status. 
Study 2:
 
 • To investigate whether the correction of malnutrition by an intensive nutritional intervention results in a decrease in SAF levels in people on PD and HD. |
| Trial Configuration | 
Study 1: longitudinal/prospective.
 
Study 2: observational non-randomized proof of principle study.
 |
| Setting | Outpatient secondary care setting. |
| Sample size estimate | 
Sample size Study 1: The primary outcome of the study is one-year survival in relation to increased SAF levels in people on HD and PD. With a power of 80%, a two-sided alpha of 5% and an expected hazard ratio of 3.5 and 2.0 in people on PD and HD, respectively, 100 HD and 40 PD participants will be needed.
 
Sample size Study 2: Since this is an observational proof of principle study, it would be reasonable to include 40 dialysis participants (either HD or PD).
 |
| Number of participants | 
Study 1:
 
 • 100 participants undergoing maintenance HD treatment (dialysis vintage greater than 3 months). • 40 PD dialysis participants with a dialysis vintage greater than 3 months. • 30 incident participants starting either HD or PD treatment (dialysis vintage \leq 3 months). 
Study 2: 40 malnourished participants on maintenance HD and PD.
 |
| Eligibility criteria | 
HD cohort:
 
 • Age: \geq18 years (no upper age limit). • At least three dialysis sessions per week for 3 or 4 hours. • Dialysis with biocompatible membranes. |

| | |
|------------------------------|---|
| | 
 • Able to give informed consent. 
PD cohort:
 
 • Age: ≥ 18 years (no upper age limit). • Dialysis with lactate/bicarbonate-buffered solutions with different glucose concentrations as prescribed for routine clinical care. • Able to give informed consent. |

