Advanced glycation end-products (AGE) are uremic toxins markedly increased in people on dialysis. Formation of AGE starts with a non-enzymatic reaction between proteins and glucose molecules called the Maillard reaction; however, AGE are also formed more rapidly during oxidative stress with the subsequent formation of reactive carbonyl compounds like methyl glyoxal. At this point, AGE synthesis is irreversible and AGE will cross-link with tissue proteins; it seems that collagen in the skin and vascular basement membranes are especially susceptible to AGE accumulation and subsequent injury. AGE also interact with specific AGE receptors that will lead to the activation of systemic inflammation by increasing the release of cytokines and, consequently, exacerbate tissue damage (Arsov et al., 2014). Importantly, AGE are also formed in food during cooking with dry heat at high temperatures such as in frying, grilling or roasting and about 10% of ingested AGE are absorbed.

Skin autofluorescence (SAF) is a relatively new technique that measures the skin accumulation of AGE. It is a non-invasive, operator independent, quick (less than 5 minutes) and easy to perform technique that utilizes the fluorescent properties of AGE, like the extensively used collagen linked fluorescence (CLF) method, and has been validated with specific AGE measurements and CLF in skin biopsies (Oleniuc et al., 2012). It has been reported that SAF is strongly correlated with overall and cardiovascular mortality in people with diabetes and undergoing HD (Hartog et al., 2007; Graff et al., 2014). Several factors have been associated with higher SAF values in people on dialysis in cross-sectional studies, for instance, chronological age in both dialysis modalities, glucose exposure from peritoneal dialysis fluid and dialysis vintage only in people on PD and presence of diabetes in people on HD (McIntyre et al., 2010; Smit et al., 2010).

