Nevertheless, analysis of baseline data from Study 1 has identified strong associations between higher SAF and malnutrition whereas no correlations were observed between higher SAF and high dietary AGE intake. Correction of malnutrition may therefore represent a more important dietary intervention to reduce accumulation of AGE in people receiving dialysis. We further reasoned that placing people with malnutrition on a restrictive diet may worsen their malnutrition and we have therefore adapted our original research plan to include an observational study to assess the impact of correcting malnutrition on SAF by providing a dietitian supervised nutritional support intervention, which essentially involves the usual/standard dietetic care/advice provided by the NHS with some additional supervision, follow-up and approved dietary supplements (also provided by the NHS), rather than a randomised trial of dietary AGE restriction.

The results from the present project will benefit people on dialysis because they may demonstrate that the correction of malnutrition decreases the SAF levels in this population. Published observational studies suggest that reduction of SAF levels will in turn be associated with a reduction in the high morbidity and mortality rates associated with chronic dialysis and, consequently, healthcare costs. Improved survival and reduced comorbidity would also be expected to improve the quality of life of people on dialysis.

TRIAL / STUDY OBJECTIVES AND PURPOSE

PURPOSE

The purpose of the present project is to investigate the association between AGE accumulation and adverse outcomes (mainly mortality) and the impact of a dietary intervention on SAF levels in people on HD and PD.

PRIMARY OBJECTIVES

Study 1:

- To investigate whether the SAF levels increase over time in prevalent and incident HD and PD participants.
- To investigate one-year survival in relation to increased SAF levels.

Study 2:

- To investigate whether the correction of malnutrition by an intensive nutritional intervention results in a decrease in SAF levels in people on PD and HD.

SECONDARY OBJECTIVES

Study 1:

- To determine the most important factors associated with change in SAF over time.
- To investigate the association of increased SAF levels with morbidity, health-related quality of life and nutritional status.
- To investigate the association between SAF levels and changes in visual function.

Study 2:

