Once participants have given their informed consent, relevant participant characteristics will be extracted from electronic data captured in medical records and from a self-report questionnaire at baseline and will include demographic characteristics, educational level, occupation status, family history, duration of renal replacement therapy, dialysis adequacy, aetiology of CKD, medical history (e.g. history of cardiovascular disease, diabetes and hypertension), current co-morbidities, alcohol history, smoking status and current medication. For the PD participants, information regarding the type of PD and the volume of the different PD solutions will also be recorded.

The accumulation of AGE will be assessed by measuring SAF using a validated Autofluorescence Reader (AGE Reader, DiagnOptics, Groningen, The Netherlands) at baseline, 3, 6, 9 and 12 months of follow-up. The method has been previously described by Meerwaldt et al. (2005). As described in the study by Siriopol et al. (2015), "the autofluorescence reader illuminates a skin surface of 1 cm², guarded against surrounding light, with an excitation light source between 300 and 420 nm (peak excitation ≈370 nm). Light from the skin is measured with a spectrometer (AVS-USB2000, Avantes Inc., Eerbeek, The Netherlands) in the 300-600 nm range, using a 200-µm glass fibre". SAF will be measured as the ratio between emission and excitation, calculated in arbitrary units (AU), by

Page 16 of 30

Skin autofluorescence as a risk marker in people receiving dialysis
Protocol draft 4.5 Final Version 2.0 04.10.2017

This protocol is confidential and the property of the University of Nottingham. No part of it may be transmitted, reproduced, published, or used by others persons without prior written authorisation from the University of Nottingham

dividing the intensity of the fluorescent light coming from the skin (measured as area under the curve [AUC] of fluorescent wave lengths between 420 and 600 nm) by the intensity of the emitted light (measured as AUC of wave lengths between 300 and 420 nm) multiplied by 100. For each participant, three measurements will be performed on the volar surface of the lower arm at \approx 10 cm below the elbow, ensuring that the area has normal skin without visible vessels, scars or other abnormalities. For HD participants, only the non-fistula arm will be used and readings will be undertaken within the first hour of HD treatment (Siriopol et al., 2015).

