To compare baseline versus final evaluations, Wilcoxon test or paired t-test will be used in the case of dimensional variables, and McNemar test in the case of categorical variables. Intergroups comparisons will be performed using Mann Whitney test or Student t test for continuous variables and χ^2 test or Fisher's exact test for categorical variables. To determine the significance and strength of associations, Pearson's correlation coefficient will be used for analyses of associations between continuous variables and Spearman rank for nonparametric variables. Linear regression analysis will be used to identify determinants of AGE accumulation. Cox proportional hazards models will be used to investigate the prognostic value of the accumulation of AGE for predicting mortality. A p-value less than or equal to 0.05 will be considered to have statistical significance.

Sample size calculation of Study 1 was performed by using the software nQuery Advisor v.6.0.

Sample size Study 1:

The primary outcome for sample size determination is one-year survival in relation to increased SAF levels in people on HD and PD. With a power of 80%, a two-sided alpha of 5% and an expected hazard ratio of 3.5 and 2.0 in people on PD and HD, respectively (based on similar findings of the studies of Kimura et al. [2014] and Siriopol et al. [2015]), 100 HD and 40 PD participants will be needed.

Sample size Study 2

Since this is a proof of principle study, it would be reasonable to include 40 dialysis participants (either HD or PD).

Assessment of efficacy

Primary endpoints

Study 1:

- Mean change in SAF levels (AU) from baseline to 12 months of follow-up.
- One-year survival.

Study 2:

Mean change in SAF levels (AU) after 6 months of a dietitian supervised intensive nutritional support intervention

Secondary endpoints

Study 1:

- Regression coefficients for identifying factors associated with the accumulation of AGE.
- Correlation coefficients for analysing the association of SAF levels with morbidity, biochemistry, circulating AGE levels, inflammatory biomarkers, visual function, health-related quality of life and nutritional status.

Study 2:

- Changes in biochemistry, circulating AGE levels, inflammatory biomarkers, visual function, health-related quality of life and nutritional status.

Assessment of safety

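### Study 1 asks which factors go with change in SAF, but its regression names the outcome only as AGE accumulation, which in the protocol's own usage is the SAF reading

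*Combined protocol and SAP*

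**What the plan says.** The synopsis and the Secondary Objectives section set the same Study 1 aim. In the latter it reads "To determine the most important factors associated with change in SAF over time".

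The matching endpoint, in both the Study Design section and the Assessment of Efficacy section, no longer mentions change. The efficacy section has "Regression coefficients for identifying factors associated with the accumulation of AGE". The method, under Statistics, Methods, is "Linear regression analysis will be used to identify determinants of AGE accumulation". No covariates, time point or repeated-measures structure are given.

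The data would support a longitudinal analysis. SAF is read at baseline, 3, 6, 9 and 12 months, then yearly for up to five years (Study 1 data collection). Change in SAF does have a named analysis as a primary endpoint: the mean change from baseline to 12 months, compared by paired t-test or Wilcoxon test. That comparison contains no explanatory factors.

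A further secondary endpoint is "Correlation coefficients for analysing the association of SAF levels with morbidity, biochemistry, circulating AGE levels, inflammatory biomarkers, visual function" and other measures. It is explicitly about levels.

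**The concern.** The objective is longitudinal, and the regression meant to serve it does not say so. An analyst who follows the protocol's vocabulary would put the SAF reading on the left-hand side. The results would then show who has high SAF, which largely reflects differences that existed before enrolment, and they could be taken as showing whose SAF is rising.

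The protocol itself indicates that the cross-sectional question is not the new one. Its background notes that "Several factors have been associated with higher SAF values in people on dialysis in cross-sectional studies". It also reports that baseline Study 1 data have already shown associations between higher SAF and malnutrition. What the repeated readings can add is information on change. At stake is whether this secondary objective gets an answer, and whether a correlate of level is mistaken for a driver of change.

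**Working it through.** The documents contain no figure on this point; the Study 1 sample size is for survival only. The check is therefore a comparison of texts, followed by an illustration under stated assumptions.

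**What accumulation means in the protocol**

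- Background: SAF is introduced as a technique that measures skin accumulation of AGE.
- Details of Device, Description: the reader is said to measure tissue accumulation.
- Study 1 data collection: "The accumulation of AGE will be assessed by measuring SAF using a validated Autofluorescence Reader".
- Statistics, Methods: the Cox sentence directly after the regression sentence uses accumulation as the mortality predictor, and the corresponding objective is worded as increased SAF levels.
- Where change is meant, the endpoint lists say change, as in the first primary endpoint.

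A level is therefore the more natural reading, although the regression sentence does not state it.

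**What the choice of outcome does**

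Inputs: 140 participants (100 HD + 40 PD, from the protocol) and two-sided alpha 0.05. Assumed, and not in the documents: between-person SD 0.7 AU, SD of true 12-month change 0.2 AU independent of baseline, reading error SD 0.15 AU, and a factor correlated 0.3 with change and 0 with baseline. Power is by Fisher's z: atanh(r) × √(n − 3), or √(n − 4) with one covariate, against 1.96.

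1. Outcome 12-month level, no baseline term: r = 0.3 × 0.2 / √(0.49 + 0.04 + 0.0225) = 0.06 / 0.743 = 0.081. Power 16%.
2. Outcome 12-month change: r = 0.06 / √(0.04 + 2 × 0.0225) = 0.06 / 0.292 = 0.206. Power 69%.
3. Outcome 12-month level with baseline SAF as covariate: residual variance = 0.5525 − 0.49² / 0.5125 = 0.0840, so r = 0.06 / 0.290 = 0.207. Power 69%.
4. The reverse case, a factor correlated 0.3 with the true level and unrelated to change, with the unadjusted 12-month level as outcome: r = 0.3 × 0.7 / 0.743 = 0.283. It is declared a determinant 92% of the time. With change as outcome the rate would be the nominal 5%.

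**Range**

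- Change SD 0.15 to 0.3 AU and error SD 0.1 to 0.2 AU: power for the change-only factor is 11–28% against level and 38–90% against change.
- Change SD 0.6 AU, error SD 0.15 AU: r = 0.18 / √(0.49 + 0.36 + 0.0225) = 0.193 against level, power 63%; r = 0.18 / √(0.36 + 0.045) = 0.283 against change, power 93%. The gap narrows as change grows relative to between-person spread.
- A separate simulation (baseline SD 0.8 AU, no reading error, change SD 0.2 to 0.6 AU, n = 140) found a change-only factor with correlation 0.3 in 13–56% of 12-month-level analyses, about 5% of baseline-level analyses and 95–96% of change analyses.

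**The case against.** The regression sentence never says level. The endpoint lists can even be read the other way. The secondary objectives run change in SAF first and increased SAF levels second; the endpoints run accumulation first and SAF levels second. In parallel, accumulation could be the endpoint's word for change, and some background sentences use it for a process. This stands as far as it goes: a reader might infer that the plan states a regression on the level, and it does not. The outcome is undefined, and level is only the likelier reading.

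Two other strong readings also fail. A reader might infer that no analysis has change as its outcome; the first primary endpoint does, and the generic group comparisons and correlations could be applied to it. What is absent is any statement linking factors to change. A reader might also infer that the correlations with SAF levels are misdirected; they match a separate objective that is itself worded in levels.

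Finally, the power contrast rests on assumed SDs and on a level regression without baseline SAF. With baseline SAF as covariate the loss disappears (step 3), so a 12-month level on the left-hand side is not cross-sectional in itself. That is correct, but the plan names no covariates, so it does not supply that adjustment. The calculation also leaves out the up to 30 incident participants and ignores attrition.

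**Conclusion.** The point holds as a gap between objective and analysis. The objective is change. The endpoint and regression name an outcome that the protocol elsewhere equates with the SAF reading, and no named analysis relates factors to change or uses the repeated readings. Followed in its own vocabulary, the plan gives a level-based answer to a longitudinal question.

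The size is illustrative: about 16% against 69% power for a factor tied only to change, and a 92% chance of flagging a factor tied only to level. Both figures depend on the assumed SDs and correlations and on the absence of a baseline term. With change and baseline independent, as assumed, the direction holds over the whole range shown; the size of the gap does not.

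This concerns a secondary objective and is a cheap improvement. It does not affect the primary endpoints or the sample size.

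**What to change.** In the Study 1 secondary endpoints (Study Design and Assessment of Efficacy) and in Statistics, Methods, state the outcome and model for this objective:

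- Preferred: a linear mixed model of the 0, 3, 6, 9 and 12-month SAF readings, with pre-specified factors and their factor-by-time terms. This keeps the readings of participants who do not complete, in line with the section on missing, unused and spurious data.
- Simpler alternative: 12-month SAF regressed on the factors with baseline SAF as covariate. It is not identical to the mixed model. It uses two visits, drops participants without a 12-month reading, and lets a little of a level association through because baseline SAF is read with error. Under the assumptions above, the level-only factor keeps a partial r of 0.21 × (1 − 0.49 / 0.5125) / √(0.914 × 0.0840) = 0.033, where 0.914 = 1 − 0.21² / 0.5125, and is flagged about 7% of the time.

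Label any regression on baseline SAF as cross-sectional, and draw conclusions about change only from the longitudinal model. Leave the correlations with SAF levels as they are.

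The cost is a few sentences and slightly more analysis work, with no new data. Coefficients for change will look smaller than those for level.

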- Does not wish to participate.
- Renal transplant.
- Pregnancy or breast feeding or intending pregnancy.
- Expected survival less than one year (for Study 1).

Expected duration of participant participation

Participants will be participating in the Study 1 for five years and in the Study 2 for 24 months.

Removal of participants from therapy or assessments/Participant Withdrawal

Participants will be withdrawn from the study if they withdraw their consent at any point, receive a renal transplant or decline to comply with the dietetic intervention (Study 2). Female participants will be withdrawn from the study if they become pregnant.

Participants may be withdrawn from the study either at their own request or at the discretion of the Investigator. The participants will be made aware that this will not affect their future care. Participants will be made aware (via the information sheet and consent form) that should they withdraw the data collected to date cannot be erased and, with their consent, may still be used in the final analysis.

If participants fail to attend for their study visits, a member of the research team will try to contact them by telephone within 24 hours of their appointment and by written correspondence within a week of the missed appointment. Multiple attempts at contact will be made by the research team over a period of a month before stating that a participant has been lost to follow-up.

With participant consent, data that is collected prior to withdrawal will be kept and analysed as part of the data set. The date, time and reason for participant withdrawal will be documented on the case report form (CRF).

To ensure attainment of adequate numbers of participants for the analysis to be valid, the research team will attempt to recruit other participants to replace any who withdraw from the study.

Informed consent

The process for obtaining participant informed consent will be in accordance with the Research Ethics Committee (REC) guidance, Good Clinical Practice (GCP) and any other regulatory requirements that might be introduced.

The research team have both training and experience in assessing participant capacity and gaining informed consent in the clinical context.

Detailed information will be provided on the study to ensure that participants understand the purpose and potential risks involved. The study will not involve participants who are unable to represent their own interests or are particularly susceptible to coercion.

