
All participants will provide written informed consent. The Informed Consent Form will be signed and dated by the participant before they enter the study. The Investigator will explain the details of the study and provide a Participant Information Sheet, ensuring that the participant has sufficient time to consider participating or not. The Investigator will answer any questions that the participant has concerning study participation.

The decision regarding participation in the study is entirely voluntary. The Investigator or their nominee shall emphasize to them that consent regarding study participation may be withdrawn at any time without penalty or affecting the quality or quantity of their future medical care.

Informed consent will be obtained from each participant before they undergo any interventions (including physical examination and history taking) related to the study. One copy of this will be kept by the participant, one will be kept by the Investigator, and a third will be retained in the participant's hospital records.

Should there be any subsequent substantial amendment to the final protocol, which might affect a participant's participation in the study, continuing consent will be obtained using an amended Consent Form which will be signed by the participant.

TRIAL / STUDY TREATMENT AND REGIMEN

Study 1 - longitudinal/prospective study

100 participants undergoing maintenance HD treatment (dialysis vintage greater than 3 months), 40 PD participants with a dialysis vintage greater than 3 months and up to 30 incident participants starting either HD or PD treatment (dialysis vintage less than 3 months) will be recruited from the Renal Unit of the Department of Nephrology at the Royal Derby Hospital and will be followed-up for five years.

Data collection and study procedures/assessments

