The Study 1 (prospective/longitudinal) involves SAF measurements and visual function, nutritional and quality of life assessments during one year of follow-up. Therefore, there is no need for an assessment of participant compliance with the study protocol. Should the participant not complete the study day, this will be classified as a withdrawal rather than non-compliance (see Section **Participant Withdrawal**).

Compliance with the intervention of Study 2 will be evaluated by means of three 24-h dietary recalls every month (1 dialysis day, 1 non-dialysis day and 1 weekend day for the HD participants and 2 weekdays and 1 weekend day for the PD participants).

Criteria for terminating trial

Study 1 is observational and will therefore only be terminated if it becomes clear that for unforeseen reasons the study is not feasible.

The intervention in Study 2 is not expected to be associated with any adverse effects. Study 2 will therefore only be terminated if it becomes clear that for unforeseen reasons the study is not feasible.

TRANSPORT AND STORAGE OF THE TISSUES

Blood samples (10 mL) will be collected at intervals as described and centrifuged. At least 2 mL of serum and 2 mL of plasma will be stored at -80°C for future analysis.

Samples and data will be stored in a linked anonymised format. Samples will be labelled using a combination of study reference, unique study identifier and cross referenced with location code numbers to permit accurate linkage to study data and the consent form.

The master database will be held by the CI in a password encrypted file.

Where participants do not agree to the future use of the samples, they will be destroyed in accordance with the Human Tissue Act, 2004.

LABORATORY ANALYSES

Routine blood/laboratory tests will be analysed in a local NHS laboratory at the Royal Derby Hospital, which is serviced and managed according to national standards and governance frameworks. No DNA or RNA extraction will occur as part of this study. Assays for CML and inflammatory markers will be conducted in research laboratories at the University of Nottingham.

STATISTICS

Methods

Statistical analysis will be conducted by [name] (PhD student), [name] and [name]. Data management and statistical analyses will be performed using statistical software SPSS version 22.0.

Data will be presented as mean \pm standard deviation, median (percentiles 25%-75%), or percentages, as appropriate.

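### The planned ordinary Cox model has no provision for the few one-year deaths likely among 40 PD participants; Firth penalisation with continuous SAF would be a cheap improvement

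*Combined protocol and SAP*

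**What the plan says.** Under Statistics, Methods, the whole plan for the mortality analysis is one sentence: "Cox proportional hazards models will be used to investigate the prognostic value of the accumulation of AGE for predicting mortality". On software: "Data management and statistical analyses will be performed using statistical software SPSS version 22.0".

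Under Sample size Study 1 in the same section: "The primary outcome for sample size determination is one-year survival in relation to increased SAF levels in people on HD and PD". The calculation uses 80% power, two-sided 5% alpha and "an expected hazard ratio of 3.5 and 2.0 in people on PD and HD, respectively", and concludes that "100 HD and 40 PD participants will be needed".

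The Exclusion criteria include "Expected survival less than one year (for Study 1", and the withdrawal section removes participants who receive a renal transplant. Study 1 also takes "up to 30 incident participants starting either HD or PD treatment", without saying whether they enter the mortality model. Follow-up runs up to five years, but the primary survival endpoint is at one year.

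The documents do not state the expected number of deaths, whether SAF enters as groups or as a continuous value, whether PD is modelled alone or pooled with HD, which test gives the p-value, or what is done when deaths are sparse.

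**The concern.** Maximum partial likelihood, which is what an unqualified Cox model means, behaves poorly with a handful of events. If SAF is grouped and all deaths fall in one group, the likelihood has no finite maximum. The software then prints a huge log hazard ratio with a huge standard error, and the Wald p-value goes to about 1. If SAF is continuous the estimate usually exists but is biased away from zero.

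PD is where this could matter. It has its own hazard ratio and only 40 participants, and both the survival exclusion and withdrawal at transplant reduce observed deaths. At stake is whether the PD hazard ratio, part of a primary objective, can be estimated and is not exaggerated. Adjustment covariates would make the problem worse.

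**Working it through.** **1. The plan's own figure.** The 40 and 100 cannot be reproduced, because no event rate or SAF scale is given.
- Two equal groups (Schoenfeld): D = 4(1.960 + 0.842)² / (ln HR)². PD: 31.4 / 1.569 = 20.005, so 21 deaths, or 52.5% of 40. HD: 31.4 / 0.480 = 65.3, so 66 deaths, or 66% of 100.
- Hazard ratio per SD of continuous SAF: D = (1.960 + 0.842)² / (ln HR)². PD: 7.85 / 1.569 = 5.001, so 5 to 6 deaths (12.5–15% of 40). HD: 7.85 / 0.480 = 16.3, so 17 deaths (17% of 100).

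The second reading would fit 40 and 100, but the documents do not say that it was used.

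**2. Inputs.** From the documents: 40 PD participants, hazard ratio 3.5, one year. Assumed, because not given: one-year mortality m of 5%, 10%, 15% or 20% (2, 4, 6 or 8 deaths in 40), a PD-only model, and no dropout.

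**3. SAF split 20/20.** Proportional hazards gives 1 − p₁ = (1 − p₀)^3.5, with (p₀ + p₁)/2 = m. Let a = (1 − p₀)²⁰ and b = (1 − p₁)²⁰ be the chances of no deaths in the low and high groups. Then P(exactly one group empty) = a(1 − b) + b(1 − a).

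At m = 10%: p₀ = 0.0465, p₁ = 0.1535, a = 0.386, b = 0.036. The result is 0.372 + 0.022 = 0.394.

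Power comes from simulation (3,000 runs per setting, censoring at one year):

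| Assumed mortality | One group empty | Wald | Score | Likelihood ratio | Firth, profile likelihood |
|---|---|---|---|---|---|
| 5% | 58% | 0% | 4% | 13% | 4% |
| 10% | 39% | 1% | 18% | 27% | 18% |
| 15% | 23% | 5% | 29% | 32% | 27% |
| 20% | 13% | 16% | 37% | 39% | 35% |

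Firth's simulated type I error with a binary exposure was 0.9–4.7%. The empty-group probability depends on the split and on mortality. With 27/13 it is 24%, 10% and 3% at 10%, 15% and 20% mortality. With 20/20 it is 3.5% at 30% mortality and 0.1% at 50%.

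**4. One example.** With 0/20 against 5/20 deaths, the ordinary fit gives log hazard ratio about 16, standard error about 1,480 and Wald p = 0.99. On the same model the score p is 0.018 and the likelihood-ratio p 0.006, but the estimate is still infinite. Firth gives a hazard ratio of about 12 with p = 0.020.

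**5. SAF continuous, hazard ratio 3.5 per SD.** An infinite estimate occurs in 8% of runs at 5% mortality, about 2.5% at 10%, 0.3% at 15% and 0.1% at 20%. Among estimable fits, ordinary Cox overstates the mean log hazard ratio by roughly 11–13%, and Firth by 1–5%. At 10% mortality the root mean squared error falls from 1.05 to 0.81. Firth's type I error was 4.6–5.3%. The bias figure depends on mortality and on how near-infinite fits are handled: repeated simulations gave 11% to 23% for ordinary Cox. At about two deaths Firth can fall below the true value among estimable fits, so its advantage in bias is clearest at 10–20% mortality.

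**The case against.** The strongest reply is that the plan does not commit to what fails. It defines no SAF groups, names no Wald test and states no PD-only model; only the sample size is split by modality. A score test on the same ordinary model recovers nearly all the power that Firth does, without new software. If SAF is continuous, the infinite hazard ratio is already uncommon, and a bias of about a tenth is small beside the sampling error from a few deaths. All of this stands, and it limits the point to a conditional one. What it does not answer is the estimate: score and likelihood-ratio tests leave an infinite hazard ratio infinite, and they do not reduce the bias.

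The mortality range is also an assumption. Under the grouped reading, the stated 80% power would need about half the PD cohort to die within a year, and an empty group would then be very rare. But such a rate sits badly with excluding people not expected to survive the year. Incident PD participants might add deaths, but their role is not stated. Follow-up beyond one year does not serve the one-year endpoint.

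A reader might infer that the plan would report the most extreme result as no effect. That goes too far. A log hazard ratio of 16 with a standard error above 1,000 visibly signals non-estimability. Nor is non-significance always a Wald artefact. With all d deaths in one group of 20, Fisher's exact p is 2·C(20,d)/C(40,d): 9,690/91,390 = 0.106 for four deaths and 31,008/658,008 = 0.047 for five. At 5% and 10% mortality, 98% and 82% of empty-group cases have four or fewer deaths. Firth gives p = 0.045 for 0 against 4, so part of its power gain there is in patterns that an exact test would not call significant.

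**Conclusion.** The point holds conditionally, as a cheap improvement and not as an error that the plan is certain to make. If PD is modelled alone with one-year mortality of 5–20%, an equal high/low split of SAF leaves exactly one group without deaths in 58% to 13% of studies, giving an infinite hazard ratio beside a non-significant Wald p-value. With continuous SAF that outcome is uncommon, and what remains is a moderate overstatement of the log hazard ratio, roughly 11–13%, which Firth largely removes at 10–20% mortality.

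The stronger statement, that the planned PD analysis will often break down, is not supported: the documents give neither the grouping nor the death rate it needs. Low power is a separate matter. With grouped SAF, Schoenfeld's formula gives about 24% power at 10% mortality and 34% at 15%, and no choice of estimator brings this to 80%.

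**What to change.** In Statistics, Methods, after the sentence on Cox models, state that SAF enters the mortality models as a continuous variable, on a named scale (per AU or per SD), and that the PD model is fitted by Firth-penalised Cox regression with profile-likelihood confidence intervals and p-values in place of Wald ones. Say whether PD is modelled separately or pooled with HD and whether incident participants are included. Report the number of deaths beside every hazard ratio. If a high/low comparison is also shown, apply the same penalised method.

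The cost is a few lines of SAP text and, probably, one package outside SPSS 22. Estimates are slightly shrunk. Recruitment and data collection do not change.
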